### Net iAUClast assessment per Week

*Net iAUClast assessment per week = [(iAUCday1-day2 + iAUCday2-day3 + ... + iAUCdn-1,dayn) / ((date of last assessment – date of randomization + 1)/7)], where n is the day of the last assessment of GS daily average.*

The calculation of net iAUClast assessment per week is detailed in appendix 9.4.

iAUC will be positive if there is an improvement of GS daily average measurements compared to baseline and negative otherwise. If a score is missing at a post baseline visit, the iAUC will be calculated from the last non missing available assessment up to the next non missing assessment.

Net iAUC per week will be displayed by treatment group and overall.

### Partial Net iAUC

If there is a missing time point which is not a final landmark time point, the data point will be considered as missing, the net iAUC will be calculated from the last non missing available assessment up to the next non missing assessment.

For the final landmark time point (week 4 for net iAUCDay1-week4, week 8 for net iAUCDay1-week8, week 12 for net iAUCDay1-week12 or week 16 for net iAUCDay1-week16), the visit window will apply. If the final landmark time point is missing, the AUC will be considered as missing. Net iAUCday1- week4, net iAUCday1- week8, net iAUCday1- week12 and net iAUCday1- week16 will also be presented for participants who have an assessment of GS daily average at week 4, week 8, week 12 or week 16 respectively.

GS daily average data for IVMP baseline, last assessment during IVMP, baseline, last assessment during DBTP and last assessment before IVIg will be listed.

Participants who have a value below 8 Kpa at baseline will be excluded from the analysis.

### GS 3 day moving average (day-2, day-1, day 0)

GS 3 day moving average will be derived for each hand (most affected and less affected). GS moving average will be derived from the third day after the first GS daily average assessment. In case of missing value of GS daily average, GS 3 day moving average will be calculated based on the number of non-missing GS daily average values.

- Value, Change from baseline, percent change from baseline of 3-day GS moving average

On the IVMP, the actual value and change from baseline and percent change from IVMP baseline GS 3-day moving average will be summarized at last assessment for each hand (most affected and less affected).

On the DBTP, for each hand (most affected and less affected), the actual value and change from baseline and percent change from baseline GS 3 day moving average will be summarized at last assessments (as defined in 6.2.1.2). For the computation of the percent change from baseline (either at IVMP baseline or DBTP baseline), in case of value of baseline equal to 0 for GS 3-day moving average, the value of baseline for the denominator will be imputed by 1.

[REDACTED]  
[REDACTED]  
[REDACTED]  
[REDACTED]  
[REDACTED]  
I [REDACTED]  
[REDACTED]  
I [REDACTED]  
[REDACTED]

- Proportion of participants with a decrease of more than 30% from baseline over 2 consecutive days of GS 3-day moving average

For each hand (most affected and less affected), the parameter will be derived.

The date of the decrease of more than 30% from baseline over 2 consecutive days will be set as the first of the 2 days consecutive reduction of GS 3-day moving average .

The proportion of participants with a GS 3 day moving average decrease of more than 30% from baseline over 2 consecutive days of GS 3-day moving average during the following period of time:

- Start of IMP and last non missing GS 3 day moving average assessment during DBTP  
- Start of IMP and last non missing GS 3 day moving average assessment before IVIg retreatment  
will be summarized by treatment group and overall using descriptive analysis.

GS 3-day moving average data for IVMP baseline, last assessment during IVMP, baseline, last assessment during DBTP and last assessment before IVIg will be listed.

Participants who have a value of 0 at baseline will be excluded from the analysis.

### 6.5.2 Functional Ability, Arm and Hand Function, Quality of Life, and Fatigue

**MMN-RODS®**

MMN-RODS© is a questionnaire to capture activity limitations specifically in participants with MMN. It consists of 25 items that are scored as follows: 0: Unable to perform, 1: Able to perform, but with difficulty and 2: Able to perform without difficulty.

MMN-RODS will be analyzed in the SAF set, using the centile metric.

The total raw score will be calculated by summing the raw score of each item (range 0-50). If at least one item has a missing value, the total raw score will be considered as missing.

The total raw score will be transformed into a centile metric score as described in appendix 9.5. The centile metric score ranges from 0 (most severe activity and social participations limitations) to 100 (no activity and no social participation limitations).

On the IVMP, actual values and change from baseline of MMN-RODS score, using the total raw score and the centile metric will be summarized by visit.

On the DBTP, actual values and change from baseline of MMN-RODS score, using the total raw score and the centile metric will be summarized by visit (as defined in 6.2.1.2).

[REDACTED]

## 9-HPT

Analyses will be performed in the SAF set.

The 9-HPT is a quantitative test of upper extremity function. Two trials are performed for each hand (the dominant and non dominant hand). The total time to complete each trial in seconds is recorded in eCOA.

For each assessment, the 2 trials for each hand will be averaged. If at least one value is missing for the dominant or non dominant hand, the average value for the corresponding hand will be considered as missing. In case, the total time for a trial exceeds 300 seconds, this trial will be excluded from the analysis, including the baseline values.

On IVMP, actual value, change from IVMP baseline and percent change from IVMP baseline of 9-HPT average time will be summarized by visit for each hand on IMVP period.

On the DBTP, actual value and change from baseline 9-HPT and percent change from DBTP baseline of average time will be summarized by visit (as defined in 6.2.1.2) for each hand.

9-HPT data will be listed.

**EQ-5D-5L**

These analyses will be performed in SAF set.

The EuroQol 5-dimension questionnaire (EQ-5D-5L) consists of 2 parts:

- A descriptive system of 5 dimensions: mobility, self-care, usual activities, pain/discomfort and anxiety/depression. Each dimension has 5 levels of response ranging from 1 (no problem) to 5 (extreme, unable to do so)
- A 20-cm vertical visual analog scale (VAS) with endpoints 0 (the worst health you can imagine) and 100 (the best health you can imagine).

For the last assessment analysis visit during DBTP and last assessment before first IVIg retreatment analysis visits, categories of improvement will be classified as follow:

- No change: the score is equal to baseline
- Improved: the score is lower than baseline
- Worsened: the score is higher than baseline

On IVMP, the number and percentage of participants will also be summarized by level at each visit for each dimension. Actual value and change from IVMP baseline in the VAS Score will be summarized on IVMP.

On DBTP, for each dimension, the number and percentage of participants will be summarized by level at each visit (as defined in [6.2.1.2](#)). The percentage of Improvement/worsening/no change will be also displayed for the last analysis visits.

Shift tables will be created to summarize the number and proportion of participants with shifts from baseline levels to last assessment derived visit (as defined in [6.2.1.2](#)) for each dimension by treatment group and overall.

Actual value and change from baseline in the VAS Score will be summarized on DBTP.

EQ-5D-5L data will be listed.

**CAP-PRI**

These analyses will be performed in SAF set.

The CAP-PRI questionnaire includes the assessment of 15 items. Items will be scored 0 (not at all), 1 (a little bit) or 2 (a lot). The total score will be calculated by adding the scores of each item yielding a total score that ranges from 0 to 30.

The CAP-PRI total score will be re-derived in ADaM for the analysis (refer to section [6.2.1.1](#) and appendix [9.3](#)). If any item score is missing, the total score will be considered as missing.

On the IVMP, actual value and change from IVMP baseline of CAP-PRI total score will be summarized at each visit using descriptive statistics.

On the DBTP, Actual value and change from baseline of CAP-PRI total score at each visit (as defined in [6.2.1.2](#)) will be summarized at each visit using descriptive statistics.

[illegible]

## PGIC

These analyses will be performed in SAF set.

Responses to the Patient Global Impression of Change questionnaire range from 1 Very much improved to 7 Very much worse. Proportion of participants by level of improvement will be described at each visit and last assessment derived visit (as defined in 6.2.1.2). Cumulative percentage will be displayed from the worst to the best category by visit.

PGIC data will be listed.

**FSS**

These analyses will be performed in SAF.

The FSS consists of answering a short questionnaire that requires the participant to rate his or her own level of fatigue on 9 items and rated from 1 to 7, depending on how appropriate they felt the statement applied to them over the preceding week. A low value indicates that the statement is not very appropriate whereas a high value indicates agreement. For the analysis, the average FSS score, calculated as the addition of all items divided by 9 will be provided.

The average FSS total score will be re-derived in ADaM for the analysis (refer to section 6.2.1.1 and appendix 9.3). If any item score is missing, the total score will be considered as missing.

On the IVMP, actual value and change from IVMP baseline of average FSS score at each visit will be summarized.

On the DBTP, actual value and change from baseline of average FSS score at each visit (as defined in 6.2.1.2) will be summarized.

FSS data will be listed.

### 6.5.3 Health-related Productivity and Work Productivity

These analyses will be performed in SAF set.

The HRPQ questionnaire consists of 21 questions. Questions assess absenteeism, presenteeism, and total percentage of work time loss due to MMN or its treatment during the past week for work output and household chores. The following items will be considered:

- **Number of scheduled hours**

- **Hours lost due to absenteeism**

The hours lost due to absenteeism is the number of hours missed form work.

- **Hours lost due to presenteeism**

The hours lost due to presenteeism will be calculated as follows:

$$\text{Hours lost due to presenteeism} = [( \text{Scheduled hours} - \text{Hours missed form work} ) \times (\text{impact}/100)]$$

- **Total hours lost (absenteeism and presenteeism)**

The total hours lost will be calculated as follows:

$$\text{Total hours lost} = \text{Hours lost due to absenteeism} + \text{Hours lost due to presenteeism}$$

- **Percent of scheduled hours lost due to absenteeism**

The percentage of scheduled hours lost due to absenteeism will be calculated as follows:

$$\text{Percentage of scheduled hours lost due to absenteeism} = (\text{Hours missed form work} / \text{Scheduled hours}) \times 100.$$

- **Percent of scheduled hours lost due to presenteeism**

$$\text{Percentage of scheduled hours lost due to presenteeism} = [(\text{Hours lost due to presenteeism} / (\text{Scheduled hours} - \text{Hours missed form work})) \times 100]$$

If (Scheduled hours - Hours missed) form work is zero, then percent of scheduled hours lost due to presenteeism will be considered as missing.

- **Percent of total scheduled hours lost (due to absenteeism and presenteeism)**

Percentage of work time lost in total (ie, absenteeism and presenteeism) will be calculated as follows:

$$\text{Percentage of work time lost in total} = [(\text{Hours lost due to presenteeism} + \text{Hours missed form work}) / \text{Scheduled hours}] \times 100$$

Each of these 6 variables will be derived for work output and household chores activities. These variables in relation to work output will be described only for employed participants while household chores activities variables will be described for all participants.

In case of scheduled hours < hours missed from work, then all the parameters for a same participant will be set to missing: number of scheduled hours, hours lost due to absenteeism, hours lost due to presenteeism, total hours lost (absenteeism and presenteeism), percent of scheduled hours lost due to absenteeism, percent of scheduled hours lost due to presenteeism, percent of total scheduled hours lost (due to absenteeism and presenteeism).

A participant is considered employed if he/she is currently employed full-time or partially.

On IVMP, each variable will be described at each visit of the IVMP period.

On DBTP, each variable will be described at each visit and (as defined in 6.2.1.2) by treatment group and overall using descriptive statistics.

HRPQ questionnaire data will be listed.

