    - Value at each visit:
      - Hours lost due to absenteeism
      - Hours lost due to presenteeism
      - Total hours lost (absenteeism and presenteeism)
      - Percent of scheduled hours lost due to absenteeism
      - Percent of scheduled hours lost due to presenteeism
      - Percent of total scheduled hours lost (due to absenteeism and presenteeism)

These endpoints will be derived for work-related activities and household chores activities.
- **Endpoints to assess medication treatment satisfaction**
  - Treatment Satisfaction 14-Item Questionnaire for Medication (TSQM-14)
    - For each subscale (Effectiveness, Side effects, Convenience, Overall Satisfaction)
      - Value at each visit of the subscale score
- **Endpoints to assess PK, PD and immunogenicity**

Serum concentrations and PK parameters for ARGX-117:  $AUC_{0-t}$ ,  $AUC_{72h}$ ,  $AUC_{0-168h}$ ,  $AUC_{336h}$ ,  $AUC_{\infty}$ ,  $C_{max}$ ,  $C_{72h}$ ,  $C_{168h}$ ,  $T_{max}$ ,  $t_{1/2}$ ,  $V_z$  and CL

Values, change from baseline and percent change from baseline, maximum percent change from baseline, maximum decrease from baseline (applicable for free C2 and CH50 only), minimum post baseline value (applicable for free C2 and CH50 only), maximum increase from baseline, maximum post baseline value (applicable for Total C2 only) in free C2, total C2, functional complement activity (CH50) over time

- Incidence and prevalence of antidrug antibodies (ADA) against ARGX-117

[REDACTED]

- [REDACTED]  
[REDACTED]
- [REDACTED]

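### The HRPQ presenteeism percentage is named as a share of scheduled hours but divided by hours worked, so label and formula disagree and it does not add with absenteeism to the total

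*SAP*

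**What the plan says.** Section 3.2 of the SAP lists, among the HRPQ secondary endpoints, percentages of scheduled hours lost to absenteeism, to presenteeism and in total. The middle one is named "Percent of scheduled hours lost due to presenteeism". Section 6.5.3 repeats the names and gives the formulas:

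- Absenteeism and total percentages: the hours concerned divided by scheduled hours.
- Presenteeism hours: scheduled minus missed hours, multiplied by impact/100.
- Presenteeism percentage: those hours divided by scheduled minus missed hours.

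Two missing-data rules follow. For a zero denominator: "If (Scheduled hours - Hours missed) form work is zero, then percent of scheduled hours lost due to presenteeism will be considered as missing". For inconsistent answers: "In case of scheduled hours < hours missed from work, then all the parameters for a same participant will be set to missing". The second rule does not cover the case where scheduled and missed hours are equal.

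The variables are derived for work (employed participants) and for household chores (all participants), and summarised in Tables 14.2.1.59 and 14.2.1.60.

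**The concern.** Three percentages with parallel names will appear together in the same tables, and one of them has a different denominator. A reader who takes the name at face value will believe that the presenteeism figure is a share of scheduled time, and will expect it to add with absenteeism to the total. Neither holds once hours are missed and the impact score is above zero.

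The missing rule has a second effect. Someone absent for all scheduled hours leaves the presenteeism summary but stays in the other two, so the three percentages can rest on different participants at the same visit.

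**Working it through.** **Inputs.** All formulas come from SAP section 6.5.3. Write S for scheduled hours, M for hours missed and I for the impact item. I is assumed to run from 0 to 100, as the division by 100 implies. The SAP states no numerical result here, so there is no figure to reproduce; the check is algebraic, with assumed values as illustration.

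**Formulas as written.**

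- Presenteeism hours: P = (S − M) × I/100
- Absenteeism % = M/S × 100
- Presenteeism % = P/(S − M) × 100
- Total % = (P + M)/S × 100

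**Step 1, substitute P.** Presenteeism % = [(S − M) × I/100]/(S − M) × 100 = I for every S > M. The hours cancel, and the variable repeats the questionnaire item.

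**Step 2, compare with the share that the name describes.** P/S × 100 = (1 − M/S) × I. The ratio of the written value to this share is S/(S − M) when I > 0. With S = 40 it is 40/32 = 1.25 at M = 8 and 40/20 = 2 at M = 20. If M = 0 or I = 0, the two values are equal.

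**Step 3, additivity.** Absenteeism % + presenteeism % as written − total % = (M/S) × I. With P/S × 100 in place of the written formula, the difference is zero.

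The identities in steps 1 and 3 were also checked over S = 1 to 60, M = 0 to S − 1 and I = 0 to 100 in steps of 10 (20,130 combinations); they held at every point.

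**Step 4, illustrations with assumed S = 40.**

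| M | I | P (hours) | Absenteeism % | Presenteeism % as written | Sum | Total % | P/S × 100 |
|---|---|---|---|---|---|---|---|
| 0 | 50 | 20 | 0 | 50 | 50 | 50 | 50 |
| 10 | 50 | 15 | 25 | 50 | 75 | 62.5 | 37.5 |
| 20 | 50 | 10 | 50 | 50 | 100 | 75 | 25 |
| 30 | 50 | 5 | 75 | 50 | 125 | 87.5 | 12.5 |
| 36 | 90 | 3.6 | 90 | 90 | 180 | 99 | 9 |
| 40 | 50 | 0 | 100 | missing | – | 100 | 0 |

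**Step 5, effect on a group mean.** Take four assumed participants with S = 40, M = 0, 10, 20, 40 and I = 20, 40, 60, 0.

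- As written: (20 + 40 + 60)/3 = 40.0% on n = 3.
- Over scheduled hours: (20 + 30 + 30 + 0)/4 = 20.0% on n = 4.
- Mean absenteeism: (0 + 25 + 50 + 100)/4 = 43.75%.
- Mean total: (20 + 55 + 80 + 100)/4 = 63.75%, which equals 43.75 + 20.0.

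**The case against.** The strongest reply is that the denominator was chosen on purpose. The SAP writes it out and adds a zero-denominator rule that fits it. Impairment during the hours actually worked is a coherent measure, and for someone who worked no hours, missing is then the natural value. Section 3.2 only lists names, so the formula in section 6.5.3 is the only operational definition. The HRPQ scoring instructions are not in the document. All of this stands.

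A reader might therefore go too far in three ways:

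- **That the formula is wrong and the scheduled-hours share is the only right value.** The document shows that name and formula disagree; it does not settle which was meant.
- **That the tables contradict each other.** The SAP promises additivity for hours only, and there it holds. The hours variables, the absenteeism percentage and the total percentage are consistent among themselves.
- **That the most impaired participants vanish from the results.** A participant absent for all scheduled hours still counts with 100% absenteeism and 100% total.

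The reply leaves the mismatch in place. A percentage of hours worked is not a percentage of scheduled hours, and nothing elsewhere in the SAP reconciles the two. The modification history records a correction to the presenteeism hours formula in version 2.0 but none to the percentage.

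**Conclusion.** The point holds as an inconsistency between name and denominator. Followed exactly, section 6.5.3 reports the impact item under a name that promises a share of scheduled hours. When M > 0 and I > 0, the reported value exceeds that share by the factor S/(S − M), and the two component percentages exceed the total by (M/S) × I points. When S = M > 0, this variable alone is missing, while absenteeism and, with presenteeism hours evaluated as 0, the total are both 100%.

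The size in the trial's data is unknown: it depends on how often hours are missed, which the SAP does not give. The consequence is limited. This is one descriptive secondary variable, for work and for chores, in a trial without formal hypothesis testing, and no primary conclusion depends on it. It should still be corrected, because the reported number does not mean what its name says.

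**What to change.** Choose one of two routes and state it in the SAP.

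1. **Share of scheduled hours intended.** Define the variable as presenteeism hours divided by scheduled hours, times 100, for work and for household chores. Set it to 0 when S = M > 0, with presenteeism hours also set explicitly to 0 in case someone who did not work leaves the impact item blank. Replace the current missing rule with one that applies when scheduled hours are 0. Deleting the rule outright would leave 0/0 for a participant with no scheduled hours. The zero-hours guard is best written for all three percentages, since they would then share the denominator.
2. **Hours-worked measure intended.** Keep the formula and its missing rule, rename the variable *percent impairment while working* in sections 3.2 and 6.5.3 and in Tables 14.2.1.59 and 14.2.1.60, and state that it does not add with absenteeism to the total.

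The first route costs one derivation and a rerun of those two tables. Both are also marked for interim analysis 1, which the modification history shows was already run, so the SAP should note that this variable will differ from that output. The second route costs only wording and changes no value.

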#### 6.5.4 Medication Treatment Satisfaction

These analyses will be performed using the SAF set.

The Treatment Satisfaction 14-Item Questionnaire for Medication (TSQM-14) is divided into 4 subscales. These 4 subscales include the effectiveness subscale (items 1 to 3), the subscale side effects (items 4 to 8), the convenience subscale (items 9 to 11) and the global satisfaction subscale (items 12 to 14).

■	
■	
■	
■	
■	
■	
■	

The (TSQM-14) scores for each subscale range from 0 to 100 with higher scores representing higher satisfaction on that domain.

On the IVMP, actual value of each subscale score at each visit will be summarized on the IVMP. The number of participants who had a side effect (ie, score item =1) will be provided as well for side effect domain.

For each subscale, the actual value at each visit (as defined in 6.2.1.2) will be summarized by treatment group and overall on the DBTP using descriptive statistics. The number of participants who had a side effect (ie, score item =1) will be provided as well for side effect domain.

Medication treatment satisfaction data will be listed.

### 6.5.5 Summary of Efficacy Endpoints

Two Efficacy summary tables will be presented for the following endpoints: mMRC-10 sum score, mMRC-14 sum score, average mMRC-14 sum score for the 2 most important muscle groups, GS 3-day moving average for most affected hand, GS 3-day moving average for less affected hand, MMN-RODs centile score, CAP-PR1 and FSS:

- the change from baseline at last assessment before IVIg analysis visit by IVIg retreatment group for each efficacy endpoint.
- the change from baseline at last assessment before IVIg analysis visit by PGIC categories for each efficacy endpoint. PGIC categories will be defined as follows:
  - o Improved: PGIC score is 1 2 or 3 at last assessment prior to IVIg retreatment
  - o No change: PGIC score is 4 at last assessment prior to IVIg retreatment
  - o Worsened: PGIC score is 5, 6 or 7 at last assessment prior to IVIg retreatment

